Specific Aim 1: To examine in a 2-week, randomized, sham controlled, double blind trial the effect of taVNS on motor symptoms in patients with mild to moderate motor symptoms of PD.

Hypothesis: taVNS will be superior to sham stimulation on its effects on the motor section of the Movement Disorder Society Unified Parkinson's Disease Rating Scale (MDS UPDRS; primary outcome measure).

Specific Aim 2: To examine in a 2-week, randomized, sham controlled, double blind trial the effect of taVNS on cognitive symptoms in PD.

Hypothesis: taVNS will be superior to sham stimulation on its effects on a composite score of the following cognitive assessment tools: DKEFS, Stroop, Digit symbol, Digit span forward and backwards, Fixation (control), Reflexive, and saccade inhibition tasks, CAARS, PROMIS (secondary outcome measure).

Specific Aim 3: To assess safety and tolerability of taVNS in PD.

Hypothesis: Treatment with taVNS will be as well tolerated as sham stimulation on the following parameters: acute monitoring of vital signs, MDS UPDRS motor evaluations and cognition testing to evaluate for worsening PD severity, adverse events or serious adverse events assessments, and the Columbia Suicide Severity Rating Scale (CSSRS). (tertiary outcome measure)

Specific Aim 4:(exploratory aim) To evaluate effects of taVNS versus sham stimulation on biomarkers relevant to VNS neurobiology.

Hypothesis: taVNS and not sham stimulation will lead to a decrease in serum inflammatory biomarkers (TNF-alpha, and IL-6), increase in serum BDNF, and increase in resting pupil diameter.

3. Design

Overview:

This pilot study of taVNS in PD intends to prove basic concepts of acute motor and cognition improvements with taVNS in PD patients. We will accomplish this by a two-week, single site, parallel, randomized, double blinded, sham-controlled pilot study of taVNS in 35 PD patients. There will be 1 screening visit, 10 stimulation visits, and 1 follow up visit.

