taVNS vs sham stimulation		x	x	x	x	x	x	x	
pupillometry		x							
saccade					x				
Vital Signs		x	x	x	x	x	x	x	
Post-stim MDS UPDRS		x		x				x	
Monitoring AE		x	x	x	x	x	x	x	x

MDS-UPDRS- Movement Disorder Society- Unified Parkinson's Disease Rating Scale (motor portion used)

C-SSRS- Columbia-Suicide Severity Rating Scale

[figure not shown]
taVNS- transauricular vagal nerve stimulation

saccade- Fixation (control), Reflexive, and saccade inhibition tasks. This is INCLUDED in cognitive battery, but will be done as a stand-alone test on stim day 6

Cognitive Battery- DKEFS, Stroop test, Digit-Symbol test, Digit Span, saccade,

Patient reported measures- CAARS, PROMIS (fatigue, sleep related, Applied Cognitive Abilities)

Figure 1: Overview of Study Flow / Assessments

4. Eligibility Criteria

Inclusion Criteria:

Age: 40-82 y
Idiopathic Parkinson's Disease Diagnosis
Disease Stage: Hoehn and Yahr stage 2-3
Patient requires a minimum of 3 doses of levodopa daily
Willingness to be videotaped

Exclusion criteria:

Dementia or MoCa <24
PD psychosis
Ear trauma
Facial pain
TBI or clinical history of stroke
Metal implants above the shoulders
History of myocardial infarction or arrhythmia, bradycardia
Active respiratory disorder
Alcohol or substance use disorders
History of DBS or other brain surgery
Epilepsy
Pregnancy
B-Blockers, dopamine blocking agent, antiarrhythmic medication, acetylcholine esterase inhibitor, midodrine, florinef, droxidopa, or anticholinergic drugs

5. Randomization and masking

Randomization of the 35 subjects will be designed to yield an expected assignment ratio of 1:1 for taVNS and sham stimulation. Treatment assignments will be masked to the patients and to all study personnel with exception of PI and others vital to providing the actual treatment. Patients will be masked to transcutaneous stimulation of the auricular branch of the vagus nerve at the tragus, versus sham stimulation. Sham stimulation involves identical perceptual threshold finding and stimulation parameters as active stimulation, with the exception of stimulation target. Sham stimulation will be delivered to the left earlobe, a target

believed to have little to no vagal nerve innervation. A blinded MUSC Movement Disorder Neurologist will rate six videotaped MDS UPDRS examinations. Rater will be blinded to sham versus active stimulation, pre-stimulation versus post-stimulation state, and to the stimulation day of study.

6. Treatment plan

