11.2 Secondary outcomes: Cognition and Biomarkers

To examine taVNS effect on cognition, a battery of behavioral and cognitive tasks relevant to PD will be assessed. We will utilize both objective and subjective measures. We will assess baseline, midpoint, and final cognitive function.

Cognitive battery:

- 1) DKEFS (Delis-Kaplan Executive Function System) verbal fluency and switching:
10 minutes
- 2) Stroop written test: 4 minutes (including start up and instructions)
- 3) Digit symbol computer based: 4 minutes (including start up and instructions)
- 4) Digit span forward and backwards: 3 minutes
- 5) Fixation (control), Reflexive, and saccade inhibition tasks: 5 minutes (including start up and instructions)

Additional subjective patient reported measures:

- 1) CAARS (Conners' Adult ADHD Rating Scales) (3 minutes)
- 2) PROMIS Sleep-Related Impairment (1 minute), PROMIS Applied Cognitive Abilities (1 minute), PROMIS Fatigue (1 minute)

To examine taVNS effect on serum markers associated with PD and neurobiology of VNS, measures of BDNF, TNF-alpha, and IL-6 will be obtained at baseline and after completion of final stimulation session. Laboratory samples will be assayed using ELISA.

To examine whether taVNS leads to the predicted pupillary resting state dilation, Eye tracking with computerized software will be used.

Pupillometry will involve a computer-based system in which an individual will receive stimulation while software records the movements and dilation of the pupil. The system used involves a setup in which infrared cameras are used to monitor the pupil in a luminance-controlled room. Participants will look at a computer screen and be instructed to maintain gaze within a specific area of the screen. IR cameras will track and monitor pupil diameter during stimulation.

11.3 **Tertiary outcome:** Safety and Tolerability

Safety and tolerability will be monitored for mean change, at each visit, from baseline to follow up. All stimulation visits include monitoring adverse events as well as vital signs. 3 visits include C=SSRS admin, 2 visits include cognition battery, 2 visits include additional physician physical examination. The follow up visit will be one additional visit 6-14 days following stimulation to specifically monitor for delayed adverse events, and will include a physical examination. Adverse events will be documented.

12. Statistical Analysis

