14.4 Potential risks and benefits

Potential Risks of taVNS

taVNS is nothing more than transcutaneous electrical nerve stimulation (TENS) of the auricular branch of the vagus nerve that innervates the ear. Although this novel therapeutic modality is still in the development and optimization process, risks are a combination of those to be expected by both the peripheral TENS and implantable cervical VNS.

TENS devices are FDA approved for pain relief and are available over the counter. The main risks associated with TENS are electrical hazards that may result in user discomfort or injury. The unit used in these studies (Digitimer DS7AH) is a 510(k) cleared electrical stimulator that meets the rigorous electrical standards of the FDA. Skin irritation, redness, or inflammation may occur under the stimulating electrodes if TENS current is delivered for a prolonged period of time.

Implantable cervical VNS is FDA approved for the treatment of intractable epilepsy and treatment resistant depression. Cervical VNS has risks associated with the procedure of

implanting the nerve, and the surgery. None of those apply here. Cervical VNS does have some minimal risks that are due to the actual stimulation of the nerve within the neck such as skin irritation. taVNS also has associated risks that may arise from the direct brain effects stimulating the vagus nerve. These theoretical risks associated with neuromodulation of the parasympathetic nervous system would also be applicable in the administration of noninvasive taVNS. They are the following: reduction of heart rate, blood pressure, and vasovagal syncope.

There have been dozens of studies in which taVNS has been used on humans, none of them reporting adverse events. A simple PubMed search for “transcutaneous vagus nerve stimulation” shows 24 peer-reviewed articles, 15 of which have been published within the past 3 years. See below table for 10 recent publications on PubMed involving taVNS on the auricular branch of the vagus in humans:

Author, Year	Aim (subject number)	Side effects/Risks/AEs
Aihua et al. 2014	Epilepsy (n= 60)	Dizziness, drowsiness
Capone et al, 2014	Cortical excitability (n=10)	No modification of instantaneous HR, systolic BP, diastolic BP, and mean BP
Kreuzer et al, 2014	Tinnitus (n=50)	Twitching and pressure at electrode site
Rong et al, 2014	Epilepsy (n=144)	None reported
Kraus et al, 2013	taVNS/fMRI (n=16)	A bright, prickling sensation, twinge or stabbing pain

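### The safety summary in section 11.3 runs from baseline to follow-up, but vital signs are scheduled only at the ten stimulation visits, and an arm mean is insensitive to a fall in one or two patients

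*Combined protocol and SAP*

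**What the plan says.** Section 11.3 (tertiary outcome) sets one summary for all safety data: "Safety and tolerability will be monitored for mean change, at each visit, from baseline to follow up". It then says "All stimulation visits include monitoring adverse events as well as vital signs", and describes the follow-up visit as one to "specifically monitor for delayed adverse events, and will include a physical examination". Vital signs are not mentioned for that visit.

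The vital-signs row in the schedule of activities (section 3) reads "Vital Signs x x x x x x x". The seven marks fall under Visits 1, 2-4, 5, 6, 7-8, 9 and 10. The screening and follow-up cells are blank.

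Sections 6.3 and 14.5 make heart rate the leading vital sign, supplemented by blood pressure, respiration and oximetry. Specific Aim 3 hypothesises that taVNS is tolerated as well as sham, and the first parameter it lists is "acute monitoring of vital signs". Section 14.4 introduces the theoretical risks of parasympathetic modulation and lists them: "They are the following: reduction of heart rate, blood pressure, and vasovagal syncope".

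Sections 3 and 8 make Visits 1, 5 and 10 OFF-medication visits and the other stimulation visits ON. Section 12 contains no safety analysis.

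**The concern.** A change from baseline to follow-up needs a value at each end. For vital signs, neither is scheduled. The analyst would have to choose a baseline after the fact. The earliest candidate is Visit 1, which is an OFF visit and qualifies only if a reading is taken before stimulation starts. The plan does not say when in a visit readings are taken.

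The summary also does not match the question. Aim 3 asks about acute monitoring and section 14.4 names falls in heart rate and blood pressure. The background in section 1 likewise reports heart rate during one-minute stimulation periods. A change measured from an earlier visit, averaged over an arm, says little about what happened within a session to an individual. At stake is a tolerability statement resting on a vital-sign summary that was either improvised or insensitive to the events the protocol itself names.

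**Working it through.** **Reading the schedule.** The plan gives no numerical safety result to reproduce, but 11.3 states some visit counts that test whether the schedule's columns are read correctly.

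| Row | Columns marked | Count | Count in 11.3 |
|---|---|---|---|
| C-SSRS | Screening, 6, 9 | 3 | 3 |
| Cognitive battery | Screening, 9 | 2 | 2 |
| Physical exam | Screening, follow-up | 2 | 2 |
| Vital signs | 1, 2-4, 5, 6, 7-8, 9, 10 | 1 + 3 + 1 + 1 + 2 + 1 + 1 = 10 | all stimulation visits |

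The three stated counts agree. The vital-signs count agrees with section 3: "There will be 1 screening visit, 10 stimulation visits, and 1 follow up visit". Vital signs are therefore scheduled at 10 of 12 visits, and the two without them are the two ends of the interval named in 11.3. The widest available span is Visit 1 to Visit 10.

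**Medication state.** OFF: Visits 1, 5 and 10, so 3. ON: Visits 2-4 (3), 6 (1), 7-8 (2) and 9 (1), so 7. With Visit 1 as baseline:

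- Visits 5 and 10 against Visit 1 compare OFF with OFF, which is like for like.
- The seven ON visits against Visit 1 compare ON with OFF, so the within-arm change contains a medication component.
- At any given visit both arms are in the same scheduled state, so the medication component is common to both and is not a source of confounding in the taVNS-sham difference.

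**Sensitivity of an arm mean.** If k of n patients in an arm have a fall of size f at a visit and the rest do not change, the visit mean moves by k × f / n. Sections 3 and 7.1 give 15 per arm. Section 5 gives 35 patients at 1:1, so 17 or 18 per arm. The size of the fall is an assumption; the documents give none.

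- f = 30 beats/min, k = 1: 30/15 = 2.0 and 30/17 = 1.8 (30/18 = 1.7).
- f = 30, k = 2: 60/15 = 4.0 and 60/17 = 3.5.
- f = 20, k = 1: 20/15 = 1.3 and 20/17 = 1.2.

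These shifts require the reading to coincide with the fall. If readings were taken only after the session and the fall had recovered by then, the shift would be 0. Because reading times are not stated, neither case can be ruled out.

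**The case against.** The strongest reply is that the rest of the safety plan covers this. Adverse events are recorded at every stimulation visit and at follow-up, so syncope or a symptomatic fall would be captured individually, and section 13.1 gives the DSMB comparisons of adverse events. That stands, and it limits the point to falls that are not reported as adverse events. For those, the plan gives no criterion for when a vital-sign change is recorded as an event, and the report contents listed in 13.1 do not name vital signs.

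Second, the interval in 11.3 may describe the monitoring period rather than a subtraction, and the sentence covers all safety data. "2 visits include additional physician physical examination", at screening and follow-up in the schedule, and these might include vital signs. The schedule is also imperfect: it shows the Visit 10 pre-stimulation motor examination under follow-up and omits the Visit 10 blood draw that the text requires. These are fair cautions. But no section says the physical examinations include vital signs, and for vital signs the text of 11.3 and the schedule agree.

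Third, Aim 3 already calls for acute monitoring, so within-session readings may well be taken. That is not excluded, but nothing in 11.3 or section 12 uses them.

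A reader might infer more than the documents support:

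- *That the plan averages across ON and OFF visits.* It does not. The mean is taken at each visit, over patients.
- *That medication state biases the comparison with sham.* Both arms follow the same schedule.
- *That heart rate is the primary safety measure overall.* Sections 6.3 and 14.5 rank it first only among the vital signs.
- *That a mean cannot show a fall at all.* A fall common to the arm would move the mean if read at the right time.
- *That the named falls are transient.* Section 14.4 gives no duration.

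**Conclusion.** The point holds for vital signs. As scheduled, no baseline-to-follow-up change can be computed for them: 10 stimulation visits have readings, while screening and follow-up have none. Using Visit 1 as a substitute baseline would mix medication state with stimulation in the within-arm change at 7 of the 9 later stimulation visits, but not at Visits 5 and 10, and would not confound the comparison between arms. An arm mean would move by about 2 beats/min for one patient with an assumed 30 beats/min fall, and less for a smaller fall.

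The conclusion rests on the schedule and 11.3 being complete about where vital signs are taken, and on the assumed size of the fall. It does not extend to adverse events or the physical examination, which do have a follow-up assessment. Nor does it touch the primary motor analysis. It should be corrected because the stated summary does not answer Aim 3's question and nothing in section 12 replaces it.

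**What to change.** In section 11.3, treat vital signs separately from the other safety data:

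1. Replace the baseline-to-follow-up mean with within-visit change: a reading before stimulation, and readings during or after it, with the times stated.
2. Compare within-visit change between arms, and show it separately for ON and OFF visits.
3. List each patient's largest individual fall, by arm.
4. Remove follow-up as an endpoint for vital signs. Adverse events and the physical examination keep theirs.

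Add a matching timing note to the vital-signs row of the schedule, and refer to this analysis in section 12. Vital signs are already taken at every stimulation visit, so the cost is the wording and a few extra recorded readings per session. The exact number depends on how often readings are taken now, which the documents do not state. No clinical threshold or stopping rule is proposed.

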Transcutaneous auricular VNS (taVNS): Although cervical VNS is relatively safe, the risks involved in surgical implantation as well as its high cost (about \$30-50k) make it less appealing and less available as a study modality. Recently, it has been shown that VNS can be administered non-invasively through stimulating the auricular branch of the vagus nerve located in the ear¹¹⁻¹³ with a transcutaneous electrical nerve stimulation (TENS) device. Our collaborators ([name] et al.) in the MUSC Brain Stimulation Lab conducted initial safety and feasibility trials of transcutaneous auricular VNS (taVNS) in healthy adults. In these studies, there were no adverse effects of taVNS observed. Their work validates ideal parameters for delivering taVNS, suggesting that one-minute taVNS periods at 200% perceptual threshold delivered at 500 μ s 25Hz are safe and tolerable and produce regional brain changes consistent with activating the vagus nerve related brain regions involved in neuroplasticity.¹³ The same group developed and conducted a concurrent taVNS/fMRI trial and demonstrated that the neurobiological effect of taVNS mimics that of cervically implanted VNS and targets several cortical and subcortical vagus afferent pathway targets. It additionally suggested that taVNS for short time periods activates the vagus nerve (10-25Hz, average 1.8mA). No rapidly accelerated or sustained drops

in HR were seen during the one-minute taVNS stimulation periods. A follow-up study determined that the optimal parameter to modulate the parasympathetic response via taVNS was 500µs pulse width, 10 & 25Hz for 60s duration.¹³

The significance of this study lies in the novelty of stimulating the vagus nerve non-invasively, in order to increase LC-NA neuronal firing and BDNF, and to decrease neuroinflammation. Given the absence of side effects in our human pilot study, we are hopeful to explore a well tolerated treatment option with potential for neuroprotective as well as symptomatic benefits in PD.

2. Objectives

The primary objective of the study is to examine the effect of taVNS on motor symptoms in patients with mild to moderate motor symptoms of PD. The study design is a single site, parallel, randomized, sham controlled, double blinded study, administering taVNS vs sham stimulation 5 days a week for 2 weeks to 35 study subjects. Additional outcomes will be effects on cognition, safety assessments, as well as stimulation effects on relevant biomarkers.

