7.3 Review Medical History

The principal investigator or designated study physician must see the patient before randomization. The physician is responsible for fully assessing whether the patient has any of the conditions listed as contraindications, chiefly a history of myocardial infarction or

arrhythmia, bradycardia, epilepsy, metal implants above the shoulders, active respiratory disorder. The presence of any contraindicated condition or medication, which are itemized in the baseline eligibility, constitutes an exclusion criterion.

8. Stimulation Visits

At **visit 1**, MDS UPDRS motor evaluation will be videotaped in the *OFF PD medication state* (defined as at least 12 hours without PD medication).

Stimulation dosing will be assessed as above. Then taVNS or sham stimulation will occur over 1 hour. Acute pupillometry testing will be done. Then repeat MDS UPDRS motor evaluation will be videotaped (assessment of acute taVNS effect). A blinded rater will later score the modified (minus rigidity) MDS UPDRS on all videos at completion of the study.

Visits 2-4 are routine stimulation treatment visits in the *ON med state* with safety assessments, but no efficacy measures.

Visit 5 (study mid point) includes *OFF med* motor evaluation pre/post stimulation as at visit 1, in addition to the stimulation session. (used as mid point motor evaluation).

Visit 6 is a stimulation treatment visits in the *ON med* state with additional behavioral saccade testing. (used as mid point cognition marker free of practice effects, not administered at visit 5, as visit 5 is an *OFF med* visit)

Visits 7-8 are taVNS treatment visits in the *ON med state* with safety assessments, but no efficacy measures.

Visit 9 is an *ON med* stimulation visit, and includes repeat cognition battery following the stimulation session. (The cognition battery is not administered at visit 10, as visit 10 is an *OFF med* day.)

Visit 10 (final day of stimulation) includes *OFF med* motor evaluation pre/post stimulation as at visit 1, in addition to the stimulation session. Repeat blood draw.

9. Specimen Collection

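### The C-SSRS, a named Aim 3 safety measure, appears in the schedule at screening, Visit 6 and Visit 9 only, so no structured suicidality assessment follows the final session; adding it to the follow-up visit is a cheap improvement.

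*Combined protocol and SAP*

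**What the plan says.** Specific Aim 3 (section 2) lists the parameters on which taVNS is to be as well tolerated as sham. The list ends with "adverse events or serious adverse events assessments, and the Columbia Suicide Severity Rating Scale (CSSRS). (tertiary outcome measure". Sections 6.3 and 14.5 also name the C-SSRS as a safety assessment.

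Section 11.3 opens with a general statement: "Safety and tolerability will be monitored for mean change, at each visit, from baseline to follow up". It then gives frequencies by type of assessment. Adverse events and vital signs are taken at every stimulation visit; for the rest, "3 visits include C=SSRS admin, 2 visits include cognition battery, 2 visits include additional physician physical examination". The follow-up visit, 6 to 14 days after stimulation, is held "to specifically monitor for delayed adverse events, and will include a physical examination". Section 10 describes the same visit as an adverse-event check. Neither section mentions the C-SSRS there.

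In the schedule of activities (section 3), the C-SSRS row has marks under screening, Visit 6 and Visit 9. The cells for Visit 10 and follow-up are blank. Section 8 identifies the last session: "Visit 10 (final day of stimulation) includes" an OFF-medication motor evaluation and a blood draw, with no mention of the C-SSRS.

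**The concern.** The protocol adds a visit after treatment specifically to find late harms, yet the one structured suicidality instrument it uses is not given there. The last C-SSRS falls before the last session. After that, a suicidality signal reaches the data only through the general adverse-event check or a disclosure by the participant.

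Two things are at stake. First, the Aim 3 comparison of the arms on this scale would stop before treatment ends, and a report of no signal could speak only for the time up to Visit 9. Second, the method of ascertainment changes at that point, from a structured interview plus general checks to general checks alone. The change is the same in both arms, so it limits what the safety data cover and does not bias the comparison.

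**Working it through.** **1. Count.** Inputs: the C-SSRS row of the schedule, read across its nine visit columns (screening, 1, 2-4, 5, 6, 7-8, 9, 10, follow-up), and the counts stated in section 11.3.

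| Row | Columns marked | Count | Section 11.3 |
|---|---|---|---|
| C-SSRS | screening, Visit 6, Visit 9 | 3 | 3 |
| Cognitive battery | screening, Visit 9 | 2 | 2 |
| Physical exam | screening, follow-up | 2 | 2 |

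All three stated counts are reproduced. C-SSRS administrations at Visit 10 or later: 0.

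**2. Can the column positions be trusted?** The extracted grid has visible faults. The third pre-stimulation MDS UPDRS mark sits under follow-up although section 8 puts that examination at Visit 10, and the Visit 10 blood draw has no mark. These may come from the PDF reading and are not held against the plan, but they lie in the last two columns, where this point relies on blanks. Three things support the C-SSRS row:

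- Its Visit 6 mark shares a column with the stand-alone saccade test, which section 8 places at Visit 6.
- Its Visit 9 mark shares a column with the cognitive battery, which section 8 places at Visit 9.
- The displaced UPDRS mark is off by one column. If the last C-SSRS mark were also off by one, it would belong to Visits 7-8 or Visit 10; follow-up is two columns from Visit 9. So the absence at follow-up survives a one-column error, whereas the absence at Visit 10 might not.

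**3. Size in sessions.** There are 5 sessions a week × 2 weeks = 10 sessions. The documents do not say whether the Visit 9 C-SSRS comes before or after that day's stimulation, so it follows 8 or 9 of the 10.

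**4. Size in days.** Follow-up is 6 to 14 days after Visit 10. The interval from Visit 9 to Visit 10 is not stated. Assuming weekday sessions without other breaks:

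- Visits 9 and 10 on consecutive days: 1 + 6 = 7 to 1 + 14 = 15 days from the last C-SSRS to follow-up.
- A weekend between them (for example, a Tuesday start): 3 + 6 = 9 to 3 + 14 = 17 days.

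On any calendar, the whole interval from Visit 10 to follow-up has no C-SSRS.

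**The case against.** The strongest reply is that section 11.3 is consistent as written. A reader might infer from its opening sentence that a C-SSRS change from baseline to follow-up is promised and cannot be computed. The documents do not support that: the sentence is about safety and tolerability in general, and the sentences after it give each type of assessment its own frequency. The cognitive battery is also an Aim 3 safety measure and also ends at Visit 9. This objection stands, and no contradiction is claimed.

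A reader might also infer that suicidality goes unmonitored after Visit 9. It does not. Adverse events are checked at Visit 10 and at follow-up in the same way as before, follow-up adds a physical examination, section 6.3 has patients and caregivers asked about non-routine medical contacts, and section 13.3 acts on a disclosure at any point in a study visit. This stands too; the gap is in the structured scale only. The documents give no figure for how much less a general check would detect.

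Third, the risks that section 14.4 attributes to vagal neuromodulation are cardiovascular, and nothing in the protocol singles out the post-stimulation period for suicidality. With 35 participants allocated 1:1, about 17 or 18 per arm, one more C-SSRS will not support a formal comparison. Both remarks are fair and keep the severity low. They do not explain why an instrument chosen as an Aim 3 measure is left out of the visit meant for late harms. Section 8 explains why the cognitive battery is not given at Visit 10 (an OFF-medication day), but no reason is offered for the C-SSRS at follow-up.

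**Conclusion.** The point holds as a minor gap in safety ascertainment. On the schedule as extracted, the C-SSRS is given three times, none at or after the final session, and it is absent from the follow-up visit. The conclusion for follow-up is the firmer one: sections 10 and 11.3 describe that visit without the C-SSRS, and the schedule reading tolerates a one-column error. The blank at Visit 10 rests on the schedule alone, since no prose names the C-SSRS visits.

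A reader might want to express the gap as a share of the observation period. That share would depend on an assumed start day and would consist mostly of days without stimulation, so none is given. The assumption-free statement is zero C-SSRS administrations between the last session and the end of observation. The primary analysis, the sample size and the allocation are unaffected.

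**What to change.** - **Schedule of activities and section 10:** add the C-SSRS to the follow-up visit.
- **Section 11.3:** change the stated number of C-SSRS visits from three to four and name them: screening, Visit 6, Visit 9 and follow-up. Naming them in prose also removes the reliance on the table.
- **Keep Visits 6 and 9.** Moving either one to hold the total at three would give up coverage during treatment.
- **Reporting, section 11.3:** state, for each arm, the number of participants with new or worse ideation or behaviour versus screening, through follow-up, presented descriptively. Any positive answer is already covered by section 13.3, which needs no change.

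The cost is a few minutes of interview at an in-person visit that already includes an adverse-event check and a physical examination, plus the wording changes. No new visit or staff is needed.
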